Missing data	When aggregating “unknown” and “not provided”, count them collectively as “unknown/not provided”. Of note, separate “unknown” and “not provided” for “medical history” and “allergy history”.

MedDRA	Use MedDRA/J Version 21.0. Count PTs for aggregation and use primary for SOC.
Adverse events	Adverse events for which the “relationship” column with CELSENTRI Tablets is not checked or “no relationship” is checked among the events that occurred on or after the first administration date of the drug, plus, the adverse reactions that are defined below. But the decision is based on the ViiV Healthcare’s company assessment. Of note, they also include the event for which you can’t decide whether it occurred on the first administration date of CELSENTRI Tablets because of unknown date even after <General Definitions> “Date conversion” resulting from its inarticulate onset date. Overlapped events with the same PT in a patient should be counted as one event in accordance with <General Definitions> “Integration process”.
Adverse reactions	The events for which the relationship with CELSENTRI Tablets cannot be ruled out. The decision is based on ViiV Healthcare K.K.’s company assessment.
Serious adverse events	“Serious” events in the seriousness criteria among the above “adverse events”. The decision is based on ViiV Healthcare K.K.’s company assessment.
Co-administration	Co-administration refers to a drug concomitantly used for at least a day. Of note, if only one date is overlapped when two anti-HIV drugs are used on the same day (as the first administration for one and the final administration for the other), it should be regarded as “replacement” and not counted as a concomitant drug.
Integration process	Take the following integration process per PT.
	<When the events occurred on the same date>
[Seriousness]	Integrate into a more severe event.
[Relationship]	The same years: Integrate into the final year when the relationship was observed. Different years: Integrate into the final year.
[Outcome (outcome confirmation date)]	The same year: Death>Not recovered>Recovered with sequela>Unknown>Recovering>Recovered>Not provided Different years: Integrate into the final year.
	Of note, when the onset date is unknown or not provided, the event with the onset date should be selected.
	<When the events occurred on different dates>
[Onset date]	Select the initial onset date.
[Seriousness]	Integrate into a more severe event.

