[Relationship]	Integrate into the date of the “related” event.
[Outcome (outcome confirmation date)]	The same year: Death>Not recovered>Recovered with sequela>Unknown>Recovering>Recovered>Not provided Different years: Integrate into the final year.
	Of note, when the onset date is unknown or not provided, the event with the onset date should be selected.
	<Processing order> Process [1]: Events which occurred in the same year and on the same date Process [2]: Events which occurred in different years but on the same date Process [3] Events which occurred in the same year but on different dates Process [4] Events which occurred in different years and on different dates.
Test	Exclude “unknown”, “not provided” and “not assessable” from test. Do not conduct a test for the items with multiple answers. When χ^2 test is conducted and the degree of freedom (DF) is 1, conduct Fisher’s exact test as well for the item.

<Handling of items>

Number of sites for the survey	Department codes (per contract) are included in the DCF site code. Count the number of site as one.
Primary disease	Give priority to "1=HIV Infection" throughout a year. "AIDS" should be regarded as "HIV Infection" in "2. Others". Others should be "Others". [Stratification] HIV Infection, Others
Sex	Use the value in the CRF at the first administration of CELSENTRI Tablets. [Stratification] Men, Women
Presence/absence of pregnancy	Patients who receive CELSENTRI Tablets for at least one day during pregnancy (if the date of last menstrual period (LMP) is unknown after LMP, see Week 0 of pregnancy or later; if both are unknown, see the pregnancy diagnosis date or later) among the patients in "Sex:3" (Pregnancy: present). Include the cases with "Women" in "Sex". [Stratification] Absence, Presence, Unknown/not provided

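### For one event reported on forms of different years, the SAP takes the last form's causality without condition, so as written a blank or 'not related' can displace an earlier 'related'

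*SAP*

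**What the plan says.** The SAP's General Definitions, under Integration process, merge repeated records of one preferred term (PT) in a patient. For relationship there are three rules:

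- Same onset date, same year: "The same years: Integrate into the final year when the relationship was observed".
- Same onset date, different years: "Different years: Integrate into the final year".
- Different onset dates, with no distinction by year: "Integrate into the date of the “related” event".

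Seriousness follows "Integrate into a more severe event" in both date branches. Outcome takes the final year across years in both branches. The merges run in a fixed order, and the second step is "Process [2]: Events which occurred in different years but on the same date", ahead of both different-date steps.

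Adverse reactions are defined as "The events for which the relationship with CELSENTRI Tablets cannot be ruled out", and "The decision is based on ViiV Healthcare K.K.’s company assessment". The definition of adverse events places on the non-ADR side those for which the relationship column "is not checked or “no relationship” is checked among the events" from first administration onward. It then adds that company assessment decides.

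Protocol section 8.2(1) makes common ADRs and ADR incidence the primary safety items. In the SAP, Attachment Form 2 tabulates ADRs using the Integration process.

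**The concern.** The cell at issue is one that this survey expects. Under Protocol section 5.4 data are entered yearly, under 5.2(1) continuing patients are re-enrolled from their previous forms, and under section 6 enrolment runs from April 2009 to March 2017. A persisting event can therefore appear on several forms with one onset date.

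In that cell the condition on an observed relationship is absent. Two consequences follow from the text as written. First, a blank on the last form can displace an earlier 'related', although a blank is not a reassessment. Second, ADR status can depend on date recording: if two forms give onset dates one day apart, 'related' is kept; if the dates are identical, it may be lost.

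ADR status feeds the incidence tables by patient background, the table of days to first ADR and, through Protocol section 7.10, the tabulations by causality for the priority items (immune competence, liver, cardiovascular). Only events repeated on later forms are exposed, so any misclassification would fall on persisting events.

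**Working it through.** The plan gives no figure on this point, so there is none to reproduce. The check applies the rules literally to two records of one PT, the first 'related' and the second 'not related' or blank.

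| Onset dates | Form years | Relationship rule | Result |
|---|---|---|---|
| same | same | record in which a relationship was seen | ADR kept |
| same | different | final year | **not an ADR** |
| different | same | the related event | ADR kept |
| different | different | the related event | ADR kept |

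If the order is reversed (not related or blank first, related second), all four cells give an ADR. Compared with a rule that keeps 'related' everywhere, only one cell differs, and only downwards.

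**Order of processing.** The same-date, different-year merge is step 2. A 'related' value dropped there returns in steps 3 or 4 only if another record of that PT, with a different onset date, is itself related. Example: year 1 related and year 2 not related with one onset date, then year 3 not related with another onset date. After step 2 no related record remains, and the result is not an ADR.

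**More than two forms.** For *k* annual records with one onset date, each related or not related:

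- sequences with at least one 'related': 2^k − 1
- of these, sequences that end in 'not related': 2^(k−1) − 1
- k = 2: 1 of 3; k = 3: 3 of 7; k = 4: 7 of 15

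These count patterns. They are not probabilities.

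**Size.** The share of ADR events lost is c × q. Here c is the share of ADRs repeated on a later form with the same onset date, and q is the share of those whose last form is not 'related'. The documents give neither. Under purely assumed values:

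- c = 5%, q = 5%: 0.05 × 0.05 = 0.25%
- c = 20%, q = 20%: 0.20 × 0.20 = 4%
- c = 40%, q = 50%: 0.40 × 0.50 = 20%

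This spread shows only that the size is undetermined. The effect on patient-level incidence is a further step away, because a patient leaves the numerator only if no other ADR remains.

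**The case against.** Four points on the other side carry weight.

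1. **Company assessment decides.** Both the adverse event and the adverse reaction definitions say so, and the SAP's Preliminary process begins with event matching under a separate specification that is not among the documents. If the company holds one current causality per matched event, few or no conflicts would reach this rule. This stands, and it is why no frequency can be given. But the SAP does not say that matching harmonises causality across years.

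2. **The order of selection and merging is open.** Attachment Form 2 can be read as merging only records already classed as adverse reactions. An earlier 'related' record would then never meet a later non-ADR record. The adverse event definition can be read the other way. This stands as an ambiguity, and the fix should settle it.

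3. **The rule may be deliberate.** One PT with one onset date on successive forms is most naturally one event under follow-up, and outcome also takes the final year. Protocol section 5.7(5) likewise has the CRO ask for the latest information on an ADR. Keeping every 'related' would retain events whose causality was later properly ruled out. This is a defensible design, but the SAP does not state it, and it cannot justify a blank displacing an assessment.

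4. **The wording may be shorthand.** The same-year rule is itself garbled, since records of one year have no final year to choose between. The different-year line may silently carry the same condition. If so, the SAP should say so, because a programmer would code the line as it stands.

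A reader might infer that the plan is shown to lower the primary ADR incidence, or that a box left unchecked by a site is enough to erase an ADR. The documents support neither: the first needs a frequency that they do not give, and the second overlooks the company's decision and the matching step.

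**Conclusion.** The point holds as a defect in the written rule. For one PT and onset date on forms of different years, the final year's relationship is taken unconditionally, whereas the other relationship rules key on the related record. As written, a blank or 'not related' on the last form can remove an earlier ADR from a primary safety item, and the processing order usually prevents its recovery.

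This rests on a literal reading and on conflicting values actually reaching the merge before ADRs are selected. If matching or company assessment resolves conflicts first, the effect may be nil. The size is unknown. A latest-assessment rule for genuine reassessments is acceptable if stated. What cannot be defended is a blank acting as a reassessment, or ADR status turning on whether two forms carry the same onset date.

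**What to change.** Replace the different-years line under Relationship (same onset date) with: *Different years: integrate into the latest year in which the relationship was observed. A blank, unknown or not-provided value never replaces an earlier 'related'; only a documented company reassessment to 'not related' may do so.*

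In addition:

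- State that this rule applies before ADRs are selected for Attachment Form 2.
- List every event that changes from 'related' to 'not related' across years.
- Report ADR incidence also with 'related in any year' counted as related.
- Keep the final year for outcome.

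The cost is one SAP line, one listing and one supplementary count. ADR counts may rise slightly. The SAP's Handling of cases records data lock on March 26, 2018. The change concerns a derivation and leaves the locked data untouched, but it may reclassify events after lock, so the listing and the supplementary count should be shown beside the main result.

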8.2 Analysis Methods

(1) Analyses related to safety evaluation

In the safety analysis set, the primary analysis items will be the occurrence of common ADRs and the incidence of ADRs (proportion of patients with AEs with which Celsentri's causal

relationship could not be denied). In addition, when tabulating the incidence of ADRs by factor such as patient background characteristics, factors affecting the onset of ADRs will be also examined.

(2) Analyses related to efficacy evaluation

Efficacy parameters for anti-HIV drugs such as a CD4 count, number of HIV-RNA copies and CDC classification will be tabulated and analyzed by patient background characteristic to examine factors affecting the efficacy of Celsentri. In patients tested for tropism, the relationship with the status of tropism change will be also evaluated.

9. Organization System for the Implementation of the Survey

The survey will be conducted using the system described in Appendix 3 in accordance with the procedures for the implementation of the HRD cooperative investigation (Appendix 2). The procedures for notifying ADRs, etc. are presented in Appendix 4.

This survey will be performed as a cooperative investigation by companies marketing drugs for the treatment of HIV infection^{Note 1)} using a common CRF. The common CRF for the drug use-results survey may be completed one copy for one patient even if a few anti-HIV infection drugs are coadministered during the reexamination period.

10. Name and Address of the Contractee, and the Scope of the Concerned Outsourced Activities

(1) Contractee

Address: PPD [redacted]

Name: PPD [redacted], PPD [redacted] CMIC PMS Co., Ltd.

Name of the person responsible for implementation: PPD [redacted], Postmarketing Surveillance Operation Implementation Supervisor

(2) Scope of outsource activities

- 1) Request to and contract with institutions
- 2) Issuance of a user's ID and password to each investigator
- 3) Retention of the originals of enrollment forms
- 4) Sending the copies of enrollment forms
- 5) Verification of registration and investigation items entered and sent by the investigators
- 6) Collection of the originals of CRFs
- 7) Preparation and collection of the statement of confirmation
- 8) Sending the copies of CRFs
- 9) Arranging reinvestigation items
- 10) Request for a reinvestigation
- 11) Retention of the originals of CRFs
- 12) Sending the CRFs (final version)
- 13) Data locking
- 14) Coding
- 15) Data tabulation/analyses

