Age	Calculate the Western-style age as of the initial administration date of CELSENTRI Tablets based on the date of birth. Of note, if the description only includes the year for date of birth in a site, describe it as "January 1". If it only includes the year and the month, replace it with "the first date of the month". If a "period of age" or "age" is provided in the "date of birth" column, select the "period of age" or "age" provided in the CRF when the patient was started on CELSENTRI Tablets only after confirmation that it is the data for the applicable year. [Stratification] [1] ≤14 years old, ≥15 and ≤64 years old, ≥65 years old, unknown/not provided [2] ≤9 years old, ≥10 and ≤19 years old, ≥20 and ≤29 years old, ≥30 and ≤39 years old, ≥40 and ≤49 years old, ≥50 and ≤59 years old, ≥60 and ≤69 years old, ≥70 years old, unknown/not provided
Inpatient/outpatient classification	Use the value in the CRF at the first administration of CELSENTRI Tablets. [Stratification] inpatient, outpatient, inpatient
Treatment history for HIV infection	Use the value in the CRF at the first administration of CELSENTRI Tablets. However, if an anti-HIV drug is administered prior to the initiation of CELSENTRI Tablets, select "2=present". [Stratification] Absence, Presence, Unknown/not provided
Race	Use the value in the CRF at the first administration of CELSENTRI Tablets. [Stratification] Japanese, others, unknown/not provided
Route of infection	Use the value in the CRF at the first administration of CELSENTRI Tablets. <Multiple-answers are acceptable in this column> [Stratification] Blood product, Mother-to-child transmission, Medical accident, Sexual transmission, Others, Unknown/not provided
Duration of disease	Calculate the years from infection to the first administration date. Display the minimum and the maximum as well. [Stratification] ≤1 year, >1 year and ≤2 years, >2 years and ≤3 years, >3 years and ≤4 years, ≥5 years, unknown/not provided
Medical history	Use the value in the CRF at the first administration of CELSENTRI Tablets. If there is an event that both occurred and recovered before the first administration of CELSENTRI Tablets in the 'adverse event' column, regard it as "present". [Stratification] Absence, Presence, Unknown/not provided
Presence/absence of allergy	Use the presence/absence of allergy provided in the CRF at the first administration of CELSENTRI Tablets. [Stratification] Absence, Presence, Unknown/not provided

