Total dose <cumulative>	
Count "the number of patients" by accumulating "total dose", count "the number of patients with adverse reactions" based on the "total dose" until the first adverse reaction occurred, and count "the number of adverse reactions" based on the "total dose" until the applicable adverse reaction occurred. Exclude the washout period. [Stratification] ≤360 tablets, >360 tablets and ≤730 tablets, >730 tablets and ≤1460 tablets, >1460 tablets, unknown/not provided

Continued/discontinued	
Display 'continued/suspended' of the final administration period throughout a year. [Stratification] Continued, Suspended, Unknown/not provided

Presence/absence of concomitant drugs	
If there is a drug concomitantly used in the "administration period" of CELSENTRI Tablets, select "2=present". If there is a drug concomitantly used at least for a day, select "2=present". Of note, if only one date is overlapped when two anti-HIV drugs are used on the same day (as the first administration for one and the final administration for the other), it should be regarded as "replacement" and not handled as a concomitant drug. [Stratification] Absence, Presence, Unknown/not provided

Number of concomitant drugs	
Number of types of concomitant drugs used in the "administration period" of CELSENTRI Tablets Drugs concomitantly used at least for a day. Of note, if only one date is overlapped when two anti-HIV drugs are used on the same day (as the first administration for one and the final administration for the other), it should be regarded as "replacement" and not counted as a concomitant drug. [Stratification] ≤2 drugs, ≥3 and ≤5 drugs, ≥6 drugs

Type of concomitant drugs	
Count the breakdowns of designated concomitant drugs. Of note, when a patient used multiple drugs in the same classification, count the drugs as one. <Multiple-answers are acceptable in this column> [Stratification] Anti-HIV drug, Other anti-virus drugs, Others

Number of concomitantly-used anti-HIV drugs	Number of types of anti-HIV drugs used in the “administration period” of CELSENTRI Tablets Drugs concomitantly used at least for a day. Of note, if only one date is overlapped when two anti-HIV drugs are used on the same day (as the first administration for one and the final administration for the other), it should be regarded as “replacement” and not counted as a concomitant drug. [Stratification] a single-use drug, 1 drug, 2 drugs, 3 drugs, ≥4 drugs

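### The SAP names no test that uses order, although several background items are ordered; adding a trend test beside the chi-square would recover power for monotone effects, mainly at 4 or more degrees of freedom.

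*SAP*

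**What the plan says.** The Test row of the SAP's General Definitions is the only text on testing in either document. It has three rules:

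- Values that are unknown, missing or unassessable are left out of any test.
- Items that allow more than one answer are not tested.
- Fisher's exact test is an addition that applies only "When χ^2 test is conducted and the degree of freedom (DF) is 1".

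It does not list the items to be tested and gives no significance level.

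Under Handling of items, the SAP bands several single-answer items in a natural order. Age has a coarse three-band grouping [1] and a finer eight-band grouping [2], which begins "≤9 years old, ≥10 and ≤19 years old, ≥20 and ≤29 years old, ≥30 and ≤39 years old". Number of concomitant drugs is banded "≤2 drugs, ≥3 and ≤5 drugs, ≥6 drugs". Disease duration has five bands, number of anti-HIV drugs five levels, and pre-treatment CDC class three (A/B/C), with a second scale P-0/P-1/P-2 in the same row. All of these appear in the planned table of adverse reaction incidence by patient background.

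Protocol section 1 makes factors likely to affect safety an objective. Section 8.2 (1) says that, when incidence is tabulated by factor, "factors affecting the onset of ADRs will be also examined".

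**The concern.** A chi-square on k ordered bands gives the same answer however the bands are arranged. If ADR incidence rises steadily with age or with number of drugs, the signal lies almost wholly along one direction, but the test spends k − 1 degrees of freedom looking in all of them. The p-value remains valid (apart from any small-count problem, which is a separate matter), but power is lost.

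Finding such factors is a stated aim, and it feeds the decision on whether a special survey or a postmarketing clinical study is needed. Enrolment closed on 31 March 2017, so power can now be gained only through the analysis.

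**Working it through.** **Plan's own figure.** There is none to reproduce: no sample size, alpha, power or ADR proportion is stated. Alpha 0.05 is assumed below.

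**Degrees of freedom.** For ADR yes/no, DF = known bands − 1, because unknown values are dropped.

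| Item (SAP, Handling of items) | Known bands | DF |
|---|---|---|
| Age [2] | 8 | 7 (6 bands, 5 DF, if the two bands below 20 years are empty) |
| Disease duration | 5 | 4 |
| Number of anti-HIV drugs | 5 | 4 |
| Number of concomitant drugs | 3 | 2 |
| CDC A/B/C | 3 | 2 |
| Age [1] | 3 | 2 |

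**Power when the effect lies on the trend.** Power = P(noncentral χ² with k DF and noncentrality λ exceeds the central 5% critical value). A 1-DF test has 80% power at λ = 7.85. The table gives chi-square power at that same λ, the λ at which chi-square itself reaches 80%, and the ratio of patients this implies.

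| DF | Power at λ = 7.85 | λ for 80% | Patients needed relative to trend test |
|---|---|---|---|
| 1 | 80% | 7.85 | 1.00 |
| 2 | 71% | 9.63 | 9.63/7.85 = 1.23 |
| 4 | 60% | 11.94 | 11.94/7.85 = 1.52 |
| 5 | 56% | 12.83 | 12.83/7.85 = 1.63 |
| 7 | 49% | 14.35 | 14.35/7.85 = 1.83 |

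With alpha 0.10 and the trend test again at 80%, chi-square has 71%, 61%, 57% and 52% at 2, 4, 5 and 7 DF, so the picture does not depend on the choice of alpha.

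**How linear must the effect be?** Where chi-square has 80% power, the trend test matches it if the rank scores capture 7.85/9.63 = 82% of the noncentrality at 2 DF, 7.85/11.94 = 66% at 4 DF, or 7.85/14.35 = 55% at 7 DF.

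**Illustration.** All inputs are assumed: six adult age bands with shares 12/32/32/15/7/2%, overall ADR proportion 12%, constant odds ratio per band, 40,000 simulated surveys per row.

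| N | Odds ratio per band | Chi-square | Trend |
|---|---|---|---|
| 400 | 1.4 | 56% | 75% |
| 200 | 1.4 | 34% | 47% |
| 400 | 1.2 | 20% | 31% |
| 400 | 1.1 | 10% | 12% |

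An odds ratio of 1.4 per band is large: 1.4^5 = 5.4 from the first band to the sixth.

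**No effect.** Each test alone rejects about 5% of the time. Reading an item as flagged if either test is below 5% gives about 8 to 9% with five or more bands, slightly less with three.

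**Where the trend test is worse.** In age [1], assume shares 3/87/10%, N = 400, ADR proportion 12% and an odds ratio of 2.5 in both outer bands: chi-square has about 60% power and trend about 30%. For a strong U-shape over eight equal age bands (N = 400, ADR proportion 10%), chi-square has 97% and trend 12%.

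**The case against.** The strongest objection is that the Test row is conditional. It says what to add when a chi-square is run at 1 DF; it does not say that every ordered item is tested, or that nothing else will be. Part of the table content sits in mock-ups that are not in the public documents, and the SAP's closing note allows table forms to change. A reader might infer that the ordered factors are tested solely by a 7-DF chi-square. The text does not go that far: exclusive use is read from silence, and 7 DF needs all eight bands of one of two age groupings to be occupied. What stands is that a SAP is the place to name tests, and no order-using test is named.

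Second, the protocol examines factors by tabulation. Incidence will be shown band by band, so a steady rise can be seen whatever the p-value. This stands, and it rules out saying that such a rise would simply be missed.

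Third, the gain is small for three-band items and for small effects, where both tests usually fail. This stands.

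Fourth, monotonicity is not natural everywhere. Age [1] isolates children and the elderly, whom the SAP's listings flag as special groups. This stands, and it rules out making trend the main test throughout.

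Fifth, drug counts include anything used during the administration period, so they can rise with exposure time and may include drugs started after the ADR. A sharper unadjusted test detects that artefact more readily too. This stands as a limit on interpretation.

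**Conclusion.** The point holds as a cheap improvement, not as an error. For roughly monotone effects, relying on chi-square alone takes power from 80% to about 60% at 4 DF, 56% at 5 DF and 49% at 7 DF. At 2 DF the fall is about 9 points. These comparisons rest on alpha 0.05 and on an effect that rank scores capture well; they do not depend on N or on the ADR proportion. Absolute power for this survey cannot be stated, and the simulated figures are illustrations only.

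Two stronger conclusions might be drawn and are not supported. One is that the planned tests are invalid: this point concerns power, and in the no-effect illustration chi-square rejects about 5% of the time. The other is that trend should replace chi-square: that would lose power for U-shaped patterns and for age [1].

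**What to change.** In the SAP Test row:

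1. List the items to be tested and the significance level.
2. For age [2], disease duration, number of concomitant drugs, number of anti-HIV drugs and CDC A/B/C, add a Cochran-Armitage trend test beside the chi-square. Use stratum rank as the score, exclude unknown values, and use the exact version when counts are sparse. Report the odds ratio per step with its 95% CI.
3. Score CDC A/B/C separately from P-0/P-1/P-2.
4. Keep chi-square as the test for age [1].
5. Before scoring disease duration, close the gap in its bands: a patient with more than 4 but less than 5 years belongs to none of them.

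The cost is a few lines of SAP text and code, with no new data. The SAP should also state the downsides. Two tests per item raise the chance of a false flag to about 8 to 9% if either is read at 5%, so both are exploratory. A trend test is weak for U-shaped patterns. Drug counts can rise with exposure time. The SAP records the data lock of 26 March 2018 as already past, so the trend test must be labelled post hoc if it is added after the locked data have been seen.
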